## **Statistical Analysis Plan**

Assuming a clinically meaningful effect size of 3 cm difference in the nausea VAS (primary outcome) between capsaicin and placebo groups and standard deviation of 2.5 cm, we estimate that we would require 12 subjects in each of two groups to allow for 80% power and alpha 0.05. To account for imprecision in the effect size and the unknown factor of early treatment withdrawal due to skin irritation, we planned a total sample size of 30 participants.

We evaluated baseline characteristics of the overall cohort using descriptive statistics and report discrete data as frequencies and percentages and continuous data as medians and interquartile ranges. For all outcomes, we used intention-to-treat analysis. For one patient in the capsaicin group, the nausea VAS at 30 and 60 minutes was missing; we used multiple imputation to assign these values. Analysis included Chi-square test or Fisher's exact test for unadjusted comparisons of categorical outcomes between treatment groups. Analysis also included student's t-test, or Mann-Whitney U test, as appropriate for unadjusted comparisons of continuous variables between treatment groups. A p-value <0.05 (two-tailed) was considered statistically significant for all tests. We performed all analyses using SAS 9.4 (Cary, NC) and report primary results with 95% confidence intervals (CI).

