Research team members assessed eligibility among all patients who presented with suspected CHS. Any potentially eligible female patients of childbearing age had to have a pregnancy test performed prior to enrollment. We randomized patients that provided informed consent to the experimental or control group using REDCap database (Research Electronic Data Capture, Vanderbilt University). Randomization used 1:1 allocation and stratified by gender. The treatment consisted of five grams of topical 0.1% capsaicin cream, and the placebo consisted of a moisturizing cream. The study team pre-packaged the capsaicin and placebo creams in identical single-dispensing tubes and coded each with a study identification number. The capsaicin cream and the placebo were identical in appearance and had no scent. An ED nurse applied study medication cream once to the abdomen in a uniform manner. The treating physicians, research team members, and patients were blinded to study drug allocation. In addition to study medication, patients received conventional therapy, which was determined by the treating physician independent of study enrollment.

Methods and Measurements

Research team members collected relevant patient demographic, clinical, and treatment data and entered data into a secure REDCap. We measured the intensity of the patient's nausea upon randomization and at 30- and 60-minutes following application of study medication. For nausea assessment, we used a previously validated visual analog scale (VAS) that ranged from 0 to 10 cm (10 being most severe).^{18,19} A research team member remained at the patient's bedside for the first 60 minutes to assess for any immediate adverse events. Additionally, the patient was assessed for any adverse events over the entire course of the patient's ED stay and, later, through a phone call at 30 days.

Outcomes

The primary outcome was the patient's reported nausea on the VAS at 30 minutes following study medication application. Secondary outcomes were the patient's reported nausea and percent change from baseline at 60 minutes, disposition status (hospital admission or discharge), and the need for rescue anti-emetic medication. The 30- and 60-minutes outcome assessment times were based on clinical experience that capsaicin has a rapid effect (<30 minutes) but may have a delayed maximum effect. Hospital admission included placement on observation or inpatient units.

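### The primary 30-minute VAS comparison leaves out the measured baseline and the stratification factor, and nothing shows how far it depends on one imputed capsaicin patient (minor)

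*SAP*

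**What the plan says.** The SAP's second paragraph (Statistical Analysis Plan) names Student's t-test or Mann-Whitney, "as appropriate for unadjusted comparisons of continuous variables between treatment groups". No adjusted model is named. It reports that in one capsaicin patient "the nausea VAS at 30 and 60 minutes was missing; we used multiple imputation to assign these values". It does not give the imputation variables, the number of imputations or the pooling rule, and describes no complete-case or other sensitivity run.

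The protocol shows that more information was available. Under Methods and Measurements, staff recorded each patient's "nausea upon randomization and at 30- and 60-minutes following application of study medication". Under Interventions, Randomization, and Blinding: "Randomization used 1:1 allocation and stratified by gender". Under Outcomes, the primary endpoint is the VAS level at 30 minutes. Baseline enters only through a secondary endpoint: "nausea and percent change from baseline at 60 minutes, disposition status".

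The analysis is described as already done ("We performed all analyses using SAS 9.4"), which limits what can still be changed.

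**The concern.** There are two separate losses.

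**Precision.** If baseline and 30-minute VAS are correlated, an unadjusted comparison gives up precision that already collected data would supply. In a pilot of 30, where the SAP promises 95% confidence intervals for the primary results, a narrower interval has real value. Gender was considered important enough to stratify on, yet it too is left out.

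**Dependence on one patient.** The imputed patient is about 1/15 of the capsaicin arm, and the missing data described are in that arm only. The documents do not say why the values are missing. The SAP's sample-size paragraph itself raises patients stopping early because of skin irritation, so missing at random cannot be taken for granted or checked from the text. If the result is borderline, the unseen value could settle which side of 0.05 it falls on, in either direction. The imputation could understate the effect as easily as overstate it.

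**Working it through.** **Inputs from the documents.** "Assuming a clinically meaningful effect size of 3 cm difference in the nausea VAS (primary outcome) between capsaicin and placebo groups"; "standard deviation of 2.5 cm"; two-sided alpha 0.05; 30 patients planned at 1:1; VAS bounded at 0 and 10 cm.

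**Assumptions, not in the documents.** 15 patients per arm; placebo mean 5 to 7 cm at 30 minutes; a baseline of 8 cm for the missing patient where one is needed; correlation r between baseline and 30-minute VAS of 0, 0.3 or 0.5.

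**1. The plan's own figure.** The normal approximation gives n = 2 × [2.5 × (1.96 + 0.84)/3]² = 10.9, so 11 per arm. The noncentral t gives power 0.763 at 11 and 0.802 at 12. The stated 12 per group reproduces.

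**2. Unadjusted benchmark at 15 per arm.** SE = 2.5 × √(2/15) = 0.913 cm. The 95% CI half-width is 2.048 × 0.913 = 1.87 cm. Power is 0.887 for 3 cm and 0.56 for 2 cm.

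**3. Reach of the missing value.** Moving it from 0 to 10 shifts the capsaicin mean by 10/15 = 0.67 cm, which is 22% of the 3 cm target and 0.73 of the SE.

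**4. Where it changes significance.** Complete case (14 vs 15): SE = 2.5 × √(1/14 + 1/15) = 0.929, so the smallest significant difference is 2.052 × 0.929 = 1.91 cm.

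With the missing value set to v and an observed capsaicin mean m:

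- capsaicin mean = (14m + v)/15
- capsaicin sum of squares = 13 × SD² + (14/15)(v − m)²
- placebo sum of squares = 14 × SD²
- pooled t on 28 df, solved for p = 0.05

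Smallest significant observed (14 vs 15) difference at SD 2.5, for placebo means 5, 6 and 7:

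| Missing value set to | Difference needed (cm) | Matching complete-case p |
|---|---|---|
| 0 | 1.67, 1.64, 1.62 | 0.083, 0.089, 0.093 |
| placebo mean | 1.99 | 0.041 |
| 8 (assumed own baseline) | 2.33, 2.20, 2.09 | 0.018, 0.025, 0.033 |
| 10 | 2.62, 2.47, 2.33 | 0.009, 0.013, 0.018 |

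A complete-case p between about 0.01 and 0.09 can therefore cross 0.05, depending on this patient. Other SDs:

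| SD | Complete case | Value 0 | Placebo mean | Value 10 |
|---|---|---|---|---|
| 2 | 1.52 | 1.28–1.31 | 1.59 | 1.95–2.26 |
| 3 | 2.29 | 1.97–2.04 | 2.39 | 2.72–2.99 |

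**5. At the planned 3 cm.** Take v = 10, placebo mean 5, SD 2.5, so m = 2. The capsaicin mean becomes (28 + 10)/15 = 2.53 and the difference 2.47. The total sum of squares is 81.25 + 59.73 + 87.5 = 228.48; the pooled SD is √(228.48/28) = 2.86 and the SE 1.04. Then t = 2.37 and p = 0.025. The same case gives p = 0.010 at SD 2 and 0.049 at SD 3.

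**6. Percent change at 60 minutes.** With baseline b, this patient's possible values span 1000/b percentage points, or 1000/(15b) of the arm mean: 6.7 points at b = 10, 8.3 at b = 8 and 13.3 at b = 5.

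**7. Gain from adjustment.** Simulated linear model with arm, baseline and gender (8/7 split, no gender effect credited, 26 df, 40,000 trials, SD 2.5):

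| r | SE (cm) | Power at 2 cm |
|---|---|---|
| unadjusted | 0.91 | 56% |
| 0 | 0.93 | 53.7% |
| 0.3 | 0.89 | 58.1% |
| 0.5 | 0.81 | 66.3% |

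The shortcut formula, with residual SD 2.5 × √(1 − r²), gives 60% and 68% at r = 0.3 and 0.5. It makes no charge for chance covariate imbalance, so the simulated figures are the more cautious. For 3 cm the shortcut gives power 0.912 and 0.955, against 0.887 unadjusted.

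**The case against.** The unadjusted test is valid in a randomized trial, and it matches the two-group difference on which the trial was sized. The benefit of adjustment depends on a correlation that the documents do not give: at 0.3 it is about 0.02 cm of SE and 2 points of power at 2 cm, and at zero it is a loss of about 2 points. No gain from gender is shown; leaving it out makes the test at most slightly conservative.

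On missing data, one patient is involved, and the SAP discloses the arm, time points and method. The wide band comes from the extremes. At the placebo mean the threshold moves only from 1.91 to 1.99 cm, and 3 cm survives every value. The arithmetic also fills in single values in a pooled t-test. It does not model multiple imputation, and it says nothing about Mann-Whitney, where an extreme value counts only by rank. A reader with the confidence interval could already work out the 0.67 cm maximum shift. The analysis is finished, so any addition is post hoc.

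Most of this stands, and it is why the point is minor. The band applies to the t-test only, and the ends of the scale are bounds. But knowing the maximum shift does not give the reader the p-value, because the filled-in value also changes the pooled SD. Nor does disclosing that imputation was used show how much it mattered. The undescribed imputation model adds to the case for showing the dependence.

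**Conclusion.** The concern holds as a minor point. The primary comparison uses neither baseline VAS nor gender, and the available text describes no check on the imputed patient. Neither omission invalidates the result, and bias toward capsaicin is not shown.

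The gain from adjustment ranges from slightly negative (r = 0) to about 10 points of power at 2 cm (r = 0.5). The imputed value matters only for a borderline result: observed differences of roughly 1.6 to 2.6 cm at SD 2.5. That is below the 3 cm target but plausible in a trial this small. Outside that band the conclusion stands whatever the value.

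These sizes rest on the assumed 15/15 split, placebo means and correlation. Confidence in them is moderate; the omissions themselves are plain from the text.

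**What to change.** Keep the planned unadjusted result, stating which test was used and the imputation variables, number of imputations and pooling rule. Beside it, report:

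- **An adjusted model.** A linear model of 30-minute VAS on arm, baseline VAS and gender, with imputation from the same variables and pooling by Rubin's rules. Label it post hoc; it could be primary only if set before unblinding.
- **The complete-case result.** It shares the missing-at-random assumption, so it is not a full check.
- **A two-sided range.** Set the missing value from 0 to 10 cm, marking the patient's own baseline and the placebo mean. This is the actual check; 0 and 10 are bounds, not plausible values.

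Repeat the complete-case run and the range for 60-minute VAS and for percent change at 60 minutes. None of these overrides the planned result. If significance changes within the range, say so in the conclusion.

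The cost is one model, a few reruns and a sentence. There are two downsides. Adjustment loses about 2 points of power at 2 cm if baseline is uninformative. The range can also make a borderline result look fragile. In simulations (20,000 trials per scenario; true difference 2 to 3 cm, SD 2.5, VAS clipped to 0–10, assumed baseline mean 7.5 and SD 1.5, r 0.3 or 0.5), trials significant on complete cases lost significance in 2–6% with the value at the placebo mean, 6–28% at own baseline and 16–52% at 10. Among non-significant trials, a value of 0 created significance in 21–41%. This is why the ends must be read only as bounds.

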Topical Capsaicin Cream for Treatment of Suspected Cyclical Vomiting Syndromes

NCT03223350

Date: April 5, 2017

Study Design and Setting

This randomized, double-blind, placebo-controlled pilot trial was performed at an urban academic trauma center hospital with 100,000 annual ED visits. The study was approved by the institutional review board and registered with the National Library of Medicine (NCT03223350). Research team members screened patients using the electronic medical record system. We obtained written informed consent from all participants. Patients were enrolled between December 2017 and July 2019.

All adult patients (age ≥ 18 years) presenting with a suspected exacerbation of CHS and had active vomiting or nausea in the ED were eligible. Exclusion criteria were: minors (< 18 years old), pregnancy, known allergy to capsaicin or hot peppers, those with resolution of nausea prior to randomization, outpatient use of prescription antiemetics within the past 24- hours, acute infectious or surgical abdominal conditions, and inability to provide informed consent. The original protocol excluded patients that received any antiemetic medication in the ED prior to enrollment. Half-way through the trial, we made a protocol change that removed this exclusion criteria and allowed enrollment of patients that received an antiemetic medication in the ED prior to randomization as long as nausea was still present. We made this protocol change due to the difficulty obtaining consent and enrolling symptomatic patients prior to receiving standard antiemetic therapy.

Interventions, Randomization, and Blinding

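### The primary 30-minute nausea VAS is compared without adjustment for the baseline VAS, which costs precision if the two correlate above about 0.2

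*SAP*

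**What the plan says.** The Protocol (Methods and Measurements) records the intensity of "nausea upon randomization and at 30- and 60-minutes following application of study medication". Under Outcomes, the primary endpoint is the patient's "reported nausea on the VAS at 30 minutes following study medication application", a raw value and not a change. Baseline enters only one outcome, a secondary one: "reported nausea and percent change from baseline at 60 minutes".

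On allocation, the Protocol (Interventions, Randomization, and Blinding) states: "Randomization used 1:1 allocation and stratified by gender".

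The SAP (Statistical Analysis Plan) offers Student's t-test or the Mann-Whitney U test, "as appropriate for unadjusted comparisons of continuous variables between treatment groups". The SAP text available for review describes no ANCOVA, regression or other adjusted model, either for baseline VAS or for gender. One capsaicin patient lacked the 30- and 60-minute VAS, and for that patient "we used multiple imputation to assign these values". Primary results are reported with 95% confidence intervals.

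**The concern.** The same patient scores the same scale at randomization and again 30 minutes after application. If the two scores correlate, part of the spread in the 30-minute score is predictable from baseline, and a model containing baseline removes it. The unadjusted comparison leaves it in, so the confidence interval is wider than the collected data require.

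Baseline nausea is not a stratification factor, so it is balanced by chance alone, and 15 per arm leaves room for a noticeable difference. An unadjusted estimate carries any such difference with it. The SAP describes baseline characteristics for the whole cohort and mentions no comparison by arm, so a reader cannot judge how much of a 30-minute difference was present at the start.

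This is a matter of efficiency and interpretation. The unadjusted test is unbiased over randomization, and its type I error is not in question.

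**Working it through.** **Inputs from the SAP.** Difference 3 cm, SD 2.5 cm, two-sided alpha 0.05, 80% power, 12 per group required, 30 patients planned.

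**Assumptions.** The 30 patients split 15 per arm. The correlation r is not in the documents, so 0 to 0.7 is shown. The baseline SD is not given either, so 1.5 to 2.5 cm is shown. Outcomes are taken as normal.

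**1. The plan's own figure.** At 12 per arm, SE = 2.5 × √(2/12) = 1.021 cm. The noncentral t with 22 df gives 80.2% power; 11 per arm gives 76.3%. The stated 12 per group is correct for an unadjusted t-test.

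**2. Unadjusted at 15 per arm.** SE = 2.5 × √(2/15) = 0.913 cm, with 28 df. The 95% half-width is 2.048 × 0.913 = 1.87 cm. Power at 3 cm is 88.7%, and the difference detectable with 80% power is 2.65 cm.

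**3. Adjusted for baseline VAS.** With N = 30, the model has N − 3 = 27 df and

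SE = 0.913 × √(1 − r²) × √((N − 3)/(N − 4)) = 0.913 × √(1 − r²) × √(27/26).

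For r = 0.5 this is 0.913 × 0.866 × 1.019 = 0.806 cm, and the half-width is 2.052 × 0.806 = 1.65 cm.

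| Analysis | 95% half-width (cm) | Power at 3 cm | Detectable at 80% power (cm) |
|---|---|---|---|
| Unadjusted | 1.87 | 88.7% | 2.65 |
| Adjusted, r = 0 | 1.91 | 87.5% | 2.70 |
| Adjusted, r = 0.2 | 1.87 | 88.7% | 2.65 |
| Adjusted, r = 0.3 | 1.82 | 90.3% | 2.58 |
| Adjusted, r = 0.5 | 1.65 | 94.8% | 2.34 |
| Adjusted, r = 0.7 | 1.36 | 99.2% | 1.93 |

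An unadjusted trial would need 19 per arm to match the half-width at r = 0.5: 2.028 × 2.5 × √(2/19) = 1.65 cm.

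**4. Break-even.** The variances are equal when (1 − r²) × 27/26 = 1, so r = √(1/27) = 0.19. Allowing for the slightly larger t quantile, the interval widths are equal at r = 0.20. Simulation (40,000 trials per r) gave variance ratios of 1.04, 1.00, 0.95 and 0.78 at r = 0, 0.2, 0.3 and 0.5, in line with the formula.

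**5. Adding gender.** With gender assumed unrelated to outcome, simulated power (20,000 trials per r) is 87.0%, 89.7%, 94.5% and 99.0% at r = 0, 0.3, 0.5 and 0.7.

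**6. Chance imbalance in baseline VAS.** The SE of the baseline difference is SD × √(2/15), which is 0.548, 0.730 or 0.913 cm for SD 1.5, 2.0 or 2.5 cm. The probability of an imbalance of 1 cm or more, in either direction, is 7%, 17% or 27%. If the baseline and 30-minute SDs are equal, each 1 cm of imbalance moves the raw estimate by r cm on average. With r = 0.5 and a true 3 cm benefit:

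- capsaicin starting 1 cm worse: the raw estimate averages 3 − 0.5 = 2.5 cm, with power about 78% unadjusted and 95% adjusted;
- capsaicin starting 1 cm better: the raw estimate averages 3 + 0.5 = 3.5 cm, with power about 98% unadjusted and 95% adjusted.

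The adjusted estimate averages 3 cm in both cases.

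**The case against.** The strongest reply is that nothing here is wrong. The endpoint, the test and the sample size fit one another, and at 15 per arm the unadjusted test already has 88.7% power for the difference the SAP calls clinically meaningful. All of that stands, and it is why this is a recommendation and not an error.

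The second reply is that the benefit depends on a correlation nobody has stated. That also stands. At r = 0.3 the half-width falls by only 0.05 cm, and near r = 0 adjustment is slightly worse. Requiring active symptoms at entry, and allowing physician-chosen conventional therapy, could both lower r. The trade is nevertheless uneven: one to two points of power lost at r = 0, against about six gained at r = 0.5. The sponsor can calculate r from data already held.

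Third, a 1 cm imbalance against capsaicin is an unfavourable case. Its probability is half the two-sided figure, about 3%, 9% or 14%, and most trials would show a smaller imbalance. The opposite direction helps the unadjusted test. The conclusion therefore rests on the figures averaged over randomization in the table.

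Fourth, the secondary percent change at 60 minutes does refer to baseline. It is a different endpoint at a different time, and it does not adjust the 30-minute comparison.

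Finally, the SAP is written in the past tense, and the Protocol states "Patients were enrolled between December 2017 and July 2019". A new analysis can now only support the reported result. At a true 3 cm difference, the simulated t-test and baseline-adjusted model disagreed on significance in 2.8%, 5.1%, 8.0% and 10.7% of trials at r = 0, 0.3, 0.5 and 0.7, which is a reason not to let the later analysis replace the first.

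**Conclusion.** The concern holds as a point about efficiency. The plan collects baseline VAS and leaves it out of the primary comparison. Relative to the unadjusted half-width of 1.87 cm, adjustment would widen the interval by about 2% at r = 0 (1.91/1.87) and narrow it by about 3% at r = 0.3 (1.82/1.87), 12% at r = 0.5 (1.65/1.87) and 27% at r = 0.7 (1.36/1.87).

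These figures assume 15 per arm, SD 2.5 cm, normal outcomes and complete data. The one imputed patient would change them slightly. They benchmark the t-test, and no equivalent was worked out for the Mann-Whitney option. The gain is material only if r is well above 0.2, and the documents do not settle whether it is. The validity of the unadjusted result and the sample-size calculation are not in dispute.

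**What to change.** Fit a linear model for the 30-minute VAS, and likewise for the 60-minute VAS, with treatment, baseline VAS and gender (the stratification factor) as terms. Fit it in each imputed dataset, include the same variables in the imputation model, and pool by Rubin's rules. Report the adjusted mean difference with its 95% CI beside the unadjusted result.

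Because the analyses have already been done, label this one post hoc and leave the reported primary test in place. Report the observed r and the adjusted SD as well, since a pilot trial can supply them for sizing a later one. In any follow-on trial, prespecify the adjusted model as primary.

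The cost is one extra model in SAS, with no new patients or data. It uses two degrees of freedom, and if r is near 0 it costs about one to two points of power.
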